8. ADVERSE EVENTS

8.1. Definitions

8.1.1. Adverse Event

An adverse event (AE) is defined as any untoward medical occurrence in a subject or clinical investigation subject administered a medicinal product and which does not necessarily have a causal relationship with this treatment. An AE can therefore be any unfavorable and unintended sign (including an abnormal laboratory finding), symptom or disease temporally associated with the use of a medicinal product, whether or not considered related to the medicinal product.

Planned hospital admissions and/or surgical operations for an illness or disease that existed before the subject was randomized in a clinical study are not to be considered AEs.

Adverse events or abnormal test findings will be followed until the event (or its sequelae) or the abnormal test finding resolves or stabilizes at a level acceptable to the Sponsor/investigator.

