8.1.4. Adverse Events of Special Interest (AESIs)

An adverse event of special interest (serious or nonserious) is one of scientific and medical concern specific to the Sponsor's product or program, which warrants ongoing monitoring and rapid communication by the investigator to the sponsor. The SAE/AESI form should be utilized for reporting the AESI even if a serious outcome may not apply.

In this study, injection site reactions including individual signs or symptoms at the injection site reported following study drug-administration will be collected as an AESI.

Signs or symptoms of injection site reaction will be evaluated by the Common Terminology Criteria for Adverse Events (CTCAE) criteria of Injection Site Reaction (General disorders and administration site conditions) to determine the event's grade (severity) (see Table 4).

TABLE 4: COMMON TERMINOLOGY CRITERIA FOR ADVERSE EVENTS (CTCAE) OF INJECTION SITE REACTION

Grade I:	Tenderness with or without associated symptoms (eg, warmth, erythema, itching)
Grade II:	Pain; lipodystrophy; edema; phlebitis
Grade III	Ulceration or necrosis; severe tissue damage; operative intervention indicated
Grade IV	Life-threatening consequences; urgent intervention indicated
Grade V	Death

Reference source: Common Terminology Criteria for Adverse Events (CTCAE), Version 4.0, Published 28 May 2009.

As indicated in [Section 6.4](#), if a local reaction around the injection site occurs, photographs should be obtained either by the investigator or another health care professional at first presentation and at each of the follow-up visits until the injection site reaction resolves.

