10.3. General Statistical Considerations and Definitions

10.3.1. General Statistical Methods

All study-collected data will be summarized by treatment group using descriptive statistics, graphs, and/or raw data listings. Categorical variables will be summarized using counts and percentages. Percentages are based on the number of subjects in the analysis set for whom there are non-missing data, unless otherwise specified. Continuous variables, including changes from baseline, will be summarized using descriptive statistics (n, mean, standard deviation, median and interquartile range [first and third quartiles], minimum and maximum).

A Statistical Analysis Plan will be written after finalizing of the eCRF and before database lock. The specifications in this document will detail the implementation of all the planned statistical analyses in accordance with the principal features stated in the protocol.

Statistical analyses will be carried out using SAS statistical analysis software version 9.2 or higher (SAS Institute, Inc., Cary, North Carolina, US).

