10.3.3. Analysis Windows and Baseline

The observational period for each subject includes the screening period (from Day -14 to Day -1), the EOS visit (Day 210 or withdrawal date). The time at which LDL-C levels have returned to >80% of baseline values will be the last observation. Any lab results collected after the last observation will not be included in the planned efficacy analysis. Safety events after the last observation, even if collected on the eCRF, will not be included in the planned statistical analysis. However, all data, including that reported after the defined observational period, will be included in the subject data listings.

Unless otherwise specified, for evaluations that are collected at multiple occasions prior to initiation of study drug, the last evaluation will be considered the "Baseline" evaluation for analysis.

Two samples for lipids and PCSK9 will be taken prior to initiation of study drug (one at screening and one prior to randomization on Day 1). The average value of the two samples will be used as the baseline evaluation.

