10.3.4. Missing Data Handling

Unless otherwise specified, missing data will not be imputed and will be excluded from the associated analysis.

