10.4.4.1. Adverse Events

The Medical Dictionary for Regulatory Activities (MedDRA) dictionary will be used for coding AEs. An AE (classified as preferred term) occurring during the double-blind treatment period will be counted as a treatment emergent AE (TEAE) either if it is not present at baseline or if it is present at baseline but increased in severity during the treatment period.

The number (percentage) of subjects reporting TEAEs for each preferred term will be tabulated by system-organ class, by system-organ class and severity, and by system-organ class and relationship to study drug. If more than one event occurred with the same preferred term for the same subject, the subject will be counted only once for that preferred term using the most severe or related occurrence for the summary by severity, or relationship to study drug, respectively.

Incidences of injection site reactions will also be presented by dose group (see also [Section 8.1.4](#)). Time to first injection site reaction will be analyzed. The severity and duration of injection site reactions, as well as their signs and symptoms, will also be summarized.

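### Injection site reactions still unresolved at last contact have no place in the planned duration summary, which would then describe resolved reactions only and read short

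*Protocol*

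**What the plan says.** Protocol 10.4.4.1 plans the incidence of injection site reactions by dose group, a time-to-first-reaction analysis, and this: "The severity and duration of injection site reactions, as well as their signs and symptoms, will also be summarized". SAP 3.1 repeats the sentence and adds no method. Neither document says what happens to a reaction that has not ended.

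Protocol 10.3.1 describes continuous variables by n, mean, standard deviation, median, quartiles, minimum and maximum; SAP 5.3.1 adds confidence intervals. No censored-data method is named for duration.

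The missing-data rule in Protocol 10.3.4 is general: "Unless otherwise specified, missing data will not be imputed and will be excluded from the associated analysis". SAP 5.3.4 has the same sentence. Neither the safety sections (Protocol 10.4.4.1; SAP 3.1 and 5.4.5.1) nor SAP section 7 sets it aside. For percentages, Protocol 10.3.1 states: "Percentages are based on the number of subjects in the analysis set for whom there are non-missing data, unless otherwise specified".

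Two other passages bear on when a reaction stops being observed. Protocol 8.1.1 has adverse events followed until the event "resolves or stabilizes at a level acceptable to the Sponsor/investigator", so an event can be closed without having resolved. Protocol 10.3.3 adds a cut-off: "Safety events after the last observation, even if collected on the eCRF, will not be included in the planned statistical analysis".

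**The concern.** A reaction still present at last contact has a start date but no stop date. With only the general rule to follow, a programmer would treat its duration as missing and exclude it. The excluded reactions tend to be the longest ones. This is the unfavourable direction for a safety summary, because persistence is what a reader wants to learn from a duration table, and persistence is what removes a reaction from it.

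The same rule, with the non-missing denominator for percentages, leaves adverse events that lack a severity or relationship out of those two breakdowns without showing how many there were.

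What is at stake is the description of local tolerability, one part of the safety results that SAP 5.4.4 says will help determine the Phase 3 dose.

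**Working it through.** The plan states no frequency or duration for injection site reactions, so there is no figure to reproduce. The check has three parts.

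**1. Direction.** Let D be the true duration with distribution function F, and T the time from onset to last contact, taken as unrelated to D. With T fixed, the resolved-only summary has distribution function F(t)/F(T) for t ≤ T. Since F(T) ≤ 1, this is at least F(t), so every quantile and the mean are at or below their true values. The same ordering holds if T varies between subjects. The reported maximum cannot exceed the longest follow-up.

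**2. Possible size (assumed durations).** Follow-up from injection to Day 210 is 210 − 1 = 209 days after the first injection and 210 − 90 = 120 days after the second. Assume onset on the injection day and a mixture: a share 1 − p exponential with mean 5 days, and a share p exponential with mean m.

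- True mean = 5(1 − p) + mp.
- Resolved share: F(T) = (1 − p)(1 − e^(−T/5)) + p(1 − e^(−T/m)).
- Resolved-only mean = [(1 − p)A(5) + pA(m)] / F(T), where A(μ) = μ − (μ + T)e^(−T/μ).
- Resolved-only quantile q solves F(t) = q·F(T).

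For p = 0.10, m = 180, T = 209: e^(−209/180) = 0.313; A(180) = 180 − 389 × 0.3131 = 58.2; A(5) = 5.0; F(T) = 1 − 0.10 × 0.313 = 0.969. The mean is (4.5 + 5.82)/0.969 = 10.7 days, against a true 0.9 × 5 + 0.1 × 180 = 22.5.

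| p, m (assumed) | Statistic | True | Resolved only, 209 days | Resolved only, 120 days |
|---|---|---|---|---|
| 10%, 180 days | unresolved | – | 3.1% | 5.1% |
| | mean | 22.5 | 10.7 | 7.5 |
| | upper quartile | 8.8 | 8.1 | 7.7 |
| | median | 4.0 | 3.8 | 3.7 |
| 20%, 180 days | mean | 40.0 | 16.7 | 10.2 |
| | upper quartile | 12.7 | 10.0 | 8.8 |
| | median | 4.8 | 4.3 | 4.1 |
| 10%, 60 days | mean | 10.5 | 9.7 | 8.2 |
| | upper quartile | 8.5 | 8.5 | 8.2 |
| | median | 4.0 | 4.0 | 3.9 |

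The mean is most exposed, the upper quartile less so, and the median hardly moves while most reactions are brief. For subjects followed to Day 360 the windows become 360 − 1 = 359 and 360 − 90 = 270 days. In the first scenario the resolved-only means are then 15.4 and 12.7 days, still short of 22.5 but closer.

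**3. Severity and relationship tables (assumed counts).** Take an arm of 60 in which 10 subjects have the event, 3 of them severe (3/60 = 5.0%), and 2 of the 10 have no severity recorded. After exclusion from numerator and denominator:

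- both missing were severe: 1/58 = 1.7%;
- missing at random: 3 × 0.8 = 2.4, and 2.4/58 = 4.1%;
- both missing were non-severe: 3/58 = 5.2%.

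The count can only fall, but the percentage can go either way. Worst-case assignment when both were non-severe gives 5/60 = 8.3%, an error in the other direction.

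**The case against.** The strongest objection is that no passage says unresolved reactions are dropped. Being ongoing at last contact is a known status, and calling it missing data is a reading of a general rule combined with silence. This is fair as to intent. It does not remove the problem, because no other written rule exists and the named statistics cannot use a reaction without an end date.

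The plan also limits how often the case arises. Events are followed to resolution or stabilisation, reactions are photographed at follow-up visits until they resolve (Protocol 6.4), and subjects whose LDL-C has not recovered are followed to as late as Day 360. The cut-off in Protocol 10.3.3 concerns later events and does not clearly exclude a later stop date for an earlier one. Grade II in the reaction table lists "Pain; lipodystrophy; edema; phlebitis", but that table reproduces a standard grading scale and is no evidence that lasting reactions are expected. All of this stands and bears on the size, not the direction.

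A reader might infer four stronger points, which the documents do not support:

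- **That a missing onset date removes an event from the treatment-emergent count.** An event counts "either if it is not present at baseline or if it is present at baseline but increased in severity during the treatment period", and events are recorded only from randomization (Protocol 8.2), so an event with unknown onset need not be lost. Onset matters more directly for the time-to-first-reaction analysis.
- **That harm overall is understated.** Overall treatment-emergent incidence and reaction incidence need neither severity nor relationship. Both fields are assigned by the investigator, and causality is mandatory for every adverse event of special interest (Protocol 8.3).
- **That reaction duration is the main tolerability result for dose choice.** SAP 5.4.4 refers only to efficacy and safety results in general.
- **That the two-dose arms are biased as a whole.** The shorter window applies only to reactions after the Day 90 injection, in subjects not followed past Day 210. First-injection reactions have the same window in every arm.

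**Conclusion.** The point holds as a limited one. On a literal reading of Protocol 10.3.4 and SAP 5.3.4, the duration summary covers only resolved reactions and is biased short. The direction follows from the rule, provided follow-up is unrelated to reaction length. The size cannot be computed from the documents. Under the assumed mixtures the mean could fall by about half or more (22.5 to 10.7 days) if a tenth of reactions persisted with a mean of 180 days, and by under a tenth (10.5 to 9.7 days) if the persistent ones averaged 60 days, both with 209 days of follow-up. The median changes by at most 0.7 days in the cases shown. If nearly all reactions resolve quickly, the bias is negligible.

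For severity and relationship, events with a missing value fall out of the breakdown counts, but the percentages need not be understated, and how often values will be missing is unknown.

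**What to change.** In Protocol 10.3.4 and 10.4.4.1, and in SAP 5.3.4 and 3.1:

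1. State that the exclusion rule does not apply to ongoing injection site reactions.
2. Summarise duration from onset by Kaplan-Meier, with unresolved reactions censored at last contact. Define that date in relation to the last-observation rule in Protocol 10.3.3, and say that a reaction closed as stabilised counts as unresolved. Report the median and quartiles where reached; the mean is not estimable without restriction if the longest reaction is censored.
3. Report the number of unresolved reactions per arm.
4. In the severity and relationship tables (including reaction grade), show events with a missing value in a separate missing row, with the safety population as denominator. Worst-case assignment is at most a sensitivity analysis, since it can overstate rates.

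The cost is one SAP paragraph, a matching protocol clarification and minor programming. Duration figures may look slightly less favourable. No extra data collection is needed beyond start date, stop date or ongoing status, and date of last contact.

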10.4.4.2. Laboratory Tests

Laboratory values will be summarized by treatment group, including changes and percent changes from baseline at each time point. Analyses will also be performed for each lab parameter by treatment group for incidence rates of potentially clinical significant values for subjects without potentially clinical significant value at baseline.

Numerical values of laboratory parameters from different local laboratories with different units and normal ranges will be converted to the conventional units and normalized to a standard set of reference/normal ranges. The normalization process will be performed and separated by each of the laboratory parameters.

10.4.4.3. Vital Signs

Change and percent change from baseline in vital signs will be summarized descriptively at each scheduled time point by treatment group.

10.4.4.4. Neurological Examinations

The percentage of subjects with a treatment-emergent abnormal neurological examination and the specific abnormality reported will be summarized by treatment group.

11. RECORDS RETENTION

United States Food and Drug Administration (FDA) regulations require all investigators participating in clinical drug trials to maintain detailed clinical data for one of the following periods:

- At least 2 years following the date on which a New Drug Application is approved by the FDA or
- Two years after the Sponsor notifies the investigator that no further application is to be filed with the FDA

Similarly, current European Union (EU) Directives/Regulations and International Conference on Harmonisation (ICH) guidelines collectively require that essential clinical trial documents (including case report forms) other than patient's medical files must be retained for the following time period:

The sponsor and investigator shall retain the essential documents relating to a clinical trial for at least 5 years after its completion. They shall retain the documents for a longer period, where so required by other applicable requirements or by an agreement between the sponsor and the investigator. Essential documents shall be archived in a way that ensures that they are readily available, upon request, to the competent authorities. The medical files of trial subjects shall be retained in accordance with national legislation and in accordance with the maximum period of time permitted by the hospital, institution or private practice.

- For at least 15 years after completion or discontinuation of the trial
- *Or* 2 years after the last approval of a marketing application in an ICH region and until there are no pending or contemplated marketing applications in an ICH region
- *Or* at least 2 years have elapsed since the formal discontinuation of clinical development of the investigational product

Investigators shall retain the documents for a longer period, where so required by applicable local requirements.

To comply with these requirements, the investigator will not dispose of any records relevant to this study without either (1) written permission from the Sponsor or (2) providing an opportunity for the Sponsor to collect such records. The investigator shall take responsibility for maintaining adequate and accurate hard copy source documents of all observations and data generated during this study, including any data clarification forms received from the Sponsor. Such documentation is subject to inspection by the Sponsor or its agents, the FDA and/or other regulatory agencies.

12. QUALITY CONTROL AND QUALITY ASSURANCE

12.1. Monitoring

The Sponsor has ethical, legal, and scientific obligations to carefully follow this study in accordance with established research principles and applicable regulations. The investigator, as part of his responsibilities, is expected to cooperate with the Sponsor in ensuring that the study adheres to the protocol and GCP requirements.

As part of a concerted effort to fulfill these obligations, the Sponsor's monitor will visit the center(s) during the study in accordance with the Monitoring Plan set forth for this trial. The investigator will permit the Sponsor to monitor the study as frequently as is deemed necessary and provide access to medical records/source documents to ensure that data are being recorded adequately, that data are verifiable and that protocol adherence is satisfactory.

12.2. Auditing

The Sponsor may conduct audits at the study center(s). Audits will include, but not be limited to, drug supply, presence of required documents, the informed consent process, and comparison of eCRFs with source documents. The investigator agrees to permit audits conducted at a reasonable time in a reasonable manner.

Regulatory authorities worldwide may also inspect the investigator during or after the study. The investigator should contact the Sponsor immediately if this occurs, and must permit regulatory authority inspections.

12.3. Protocol Deviations

This study will be conducted as described in this protocol, except for an emergency situation in which the protection, safety, and well-being of the subject requires immediate intervention, based on the judgment of the investigator (or a responsible, appropriately trained professional designated by the investigator). In the event of a significant deviation from the protocol due to an emergency, accident, or mistake, the investigator or designee must contact the Sponsor, or their agent, at the earliest possible time by telephone. This will allow an early joint decision regarding the subject's continuation in the study. The investigator and the Sponsor will document this decision. The IRB/EC will be informed of all protocol changes by the investigator in accordance with the IRB/EC established procedure. No deviations from the protocol of any type will be made without complying with all the IRB/EC established procedures.

The following Protocol Deviations will require additional information in the eCRF explaining why the deviation occurred and what will be done to prevent it from re-occurring:

- Injection not administered for any reason other than subject safety or withdrawal
- Wrong dose (dose concentration, wrong dose, wrong treatment, wrong regimen, wrong injection site)*
- Missed assessment as per the Schedule of Events/Assessments ([Table 3](#)) at Baseline, Days 90, 180, and 210 (EOS) visit

- Inclusion criteria violation
- Exclusion criteria violation
- Subject not adhering to protocol subject restrictions
- Subject taking any prohibited concomitant medication

*If the mis-dosing was unintended (ie, a medication error), the error should be reported as per instructions in [Section 8.4](#), Procedure for Medication Error Reporting.

13. ETHICS AND RESPONSIBILITY

This study will be conducted in compliance with the protocol, the Sponsor's standard operating procedures and/or guidelines, the FDA regulations, the ICH GCP guidelines, the Declaration of Helsinki and other local regulations, as applicable.

13.1. Informed Consent

Written informed consent will be obtained from all subjects before any study-related procedures (including any pre-treatment procedures) are performed. The investigator(s) has both ethical and legal responsibility to ensure that each subject being considered for inclusion in this study is given a full explanation of the protocol. This shall be documented on a written informed consent form (ICF), which shall be approved by the same IRB or EC responsible for approval of this protocol. Each ICF shall include the elements required by ICH, Part E6, Section 4.8 and any applicable local regulations. The investigator agrees to obtain approval from the Sponsor of any written ICF used in the study, preferably prior to submission to the IRB or EC.

Once the appropriate essential information has been provided to the subject and fully explained by the investigators (or a qualified designee) and it is felt that the subject understands the implications of participating, the subject and the investigator (or designee) shall sign the IRB- or EC-approved written ICF. The subject shall be given a copy of the signed ICF, and the original shall be filed appropriately, according to the institution. A second copy may be filed in the subject's medical record, if allowed by the institution.

13.2. Institutional Review Board/Ethics Committee

This protocol, the written ICF and any materials presented to subjects shall be submitted to the IRB or EC identified with this responsibility. Notification in writing of approval must come from the IRB or EC chairman or secretary, to the investigator, either as a letter or as a copy of the appropriate section of the IRB or EC meeting minutes where this protocol and associated ICF were discussed. The investigator will not participate in the decision. If the investigator is an IRB or EC member, the written approval must indicate such non-participation in the voting session. The investigator will submit status reports to the IRB or EC as required by the governing body. The IRB or EC must be notified by the investigator in writing of the interruption and/or completion of the study; the investigator must promptly report to the IRB or EC all changes in research (protocol amendments) and will not make such changes without IRB or EC approval, except where necessary to eliminate apparent immediate hazards to human subjects. In cases where it is necessary to eliminate immediate hazards to subjects, the IRB or EC must then be notified of the change as per local requirements. The investigator is required to maintain an accurate and complete record of all written correspondence to and received from the IRB or EC and must agree to share all such documents and reports with the Sponsor.

